4 STUDY DESIGN

4.1 OVERALL DESIGN

This study is a feasibility trial testing the ability to recruit an appropriate population (the union health fund), collect outcome measures relevant to change from using the intervention (through administrative claims data and collection of worker surveys), and process measures of implementation over a period of time considered appropriate to implement organizational changes guided by the intervention.

This is a feasibility trial evaluating procedures and success to enroll the health funds, collect data, monitor implementation of the intervention, and assess change in outcome measures in a 6-month period of time.

The health funds recruited to participate in this study will be from a convenience sample using a snowball method of recruitment. The study does not involve randomization.

This is a single arm trial with pre-post measures of change in the outcomes over a 6-month period of time. The study will attempt to collect 12-month measures if time allows.

This will be a single-site trial, as all data will be collected by the research team, although the invitations for worker survey participation will be distributed through messages from the participating union health fund. The administrative data will be shared with the Washington University researchers through a data transfer and use agreement.

The intervention is the Workplace Guidelines to Prevent Opioid and Substance Abuse for the Construction Trades. These guidelines offer ideas, resources and organizational assessments on how to develop or advance a substance use prevention program targeting policies, programs, and benefits under the employer, union and their health and welfare funds.

4.2 SCIENTIFIC RATIONALE FOR STUDY DESIGN

This is a feasibility trial to evaluate the study procedures and feasibility of recruiting and collecting the data for a future trial. As such, it was important to recruit a small number of groups from the population, and collect data for the intended period of time, but there was no need for a comparator group for the intended goal of this study.

4.3 JUSTIFICATION FOR INTERVENTION

The construction industry has one of the highest overdose rates of any industry, with the majority of those overdoses from opioids. The industry has one of the highest injury rates with many workers suffering from chronic disorders incurred from work activities. Prescription opioids have been prescribed to treat these chronic disorders. The union health fund provides the health benefits and health programs for the union members. There is a need to provide union health funds with guidance on policies, programs and benefits that may help prevent initial use of prescription opioids and treatment for members with opioid misuse and opioid use disorder. The Workplace Guidelines to Prevent Opioid and Substance Abuse for the Construction Trades are evidence-based guidelines designed for use by the construction industry. The guidelines are intended to be used by construction organizations to assess their need, and provide guidance and off the shelf resources that may be tailored for use by the organization. The overall goal of the guidelines are to reduce the incidence of opioid misuse and opioid use disorder, missed days of work due to opioid use, and increase members willingness to seek treatment if they need help.

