1 PROTOCOL SUMMARY

Title:	Improving Health and Employment Outcomes Through Workplace Opioid Policies
Grant Number:	1R34DA050044-01
Study Description:	We will implement the intervention in three local union health funds, evaluate the implementation using the RE-AIM framework, and collect the data needed to measure effectiveness of the workplace opioid guidelines. We will measure a) the health fund's adoption of policies and programs; b) opioid prescriptions, chronic opioid use, and OUD in health claims and pharmacy data; c) changes in knowledge, attitudes, and beliefs of employers, health fund administrators, and employees; and d) employee participation in employee assistance programs and healthcare recovery services.
Objectives*:	The overall aim is to evaluate the feasibility of implementing workplace opioid guidelines in the construction trades; define and collect measures of implementation and effectiveness. The primary objective is to evaluate a change in opioid misuse and opioid use disorder from medical and pharmacy claims, and worker surveys following a change in policies and programs within health funds. The secondary objective is to evaluate a change in lost time and willingness to seek help among workers who are struggling with opioid misuse or substance use problems on worker surveys.
Endpoints*:	The primary endpoints are a) the change in the proportion of workers with opioid misuse, opioid use disorder and opioid overdose: administrative data and b) in the proportion of workers with opioid misuse: worker surveys from baseline to 6-months. The secondary endpoints are a) the change in the proportion of workers with lost time: worker surveys and b) the proportion of workers who are willing to seek help: worker surveys from baseline to 6-months.
Study Population:	Participants will be members of three participating union health funds. We anticipate these unions will have 33300 members enrolled between 2019-2023, which is the period of data used for the trial. All union members of the participating health funds will be enrolled in the study. We expect the demographics of the participants will reflect the demographics of the membership, which is approximately 8% female, and 90% Caucasian. All participants will be located within the geographical region of the union membership.
Phase* or Stage:	This is a feasibility trial.

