9.4 STATISTICAL ANALYSES

9.4.1 GENERAL APPROACH

Outcome data is derived from the administrative claims and worker surveys.

Administrative claims will be collected over two periods (06/01/2019-05/31/22) and (06/01/2022-05/31/2023). All three outcomes of interest are primary outcomes. The analysis will examine the group level change of the outcome, adjusting for length of time in each period, to show a reduction in impaired health or behaviors that may be due to implementation of the intervention.

Worker surveys will be collected by member worker surveys from each health fund at two points in time. The baseline, before implementation of the intervention, and at 6-months after start of implementation. All members will be invited to complete a survey. The desired sample is 300 surveys per health fund at each time point. The outcomes are composed of one or more items in the surveys. Group level statistics will be computed as the proportion of members with a positive response to each outcome. The change in proportion by time point may be due to implementation of the intervention.

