9.4.2 ANALYSIS OF THE PRIMARY ENDPOINT(S)

- a) Administrative Claims
 - a. Outcome variables of interest
 - i. Opioid misuse- “Overlapping Rx” OR “Multiple Rx on same day, different provider”
 - ii. Chronic opioid use- more than 60 days supply in a 90 day window
 - iii. Opioid use disorder- ICD-10 T40* (Poisoning by, adverse effect of and underdosing of narcotics and psychodysleptics) &/Or ICD-10 F11* (opioid related disorders) &/or prescribed MAT (Drug name contained “methadone” or “buprenorphine”; picks up buprenorphine, suboxone, zubsolv, naltrexone, methadone, narcan, and vivitrol)
 - b. Compute statistics for baseline period (06/01/2019-05/31/2022) and follow-up (06/01/2022-05/31-2023)

- i. Categorical data will be presented as N (%), continuous data as median (25th, 75th %tile)
- c. Run comparisons between baseline and follow-up time points
 - i. Comparisons involving two categorical variables will be made using Fisher's exact test
 - ii. Comparisons involving a continuous variable and a categorical variable will be made using Wilcoxon Rank Sum test or Kruskal Wallis test

b) Worker Survey

- a. Outcome variable of interest
 - i. Opioid misuse- Participant responded yes to one of the following two questions:
 - 1. Did you use the pain medication more than prescribed, or for a longer period than prescribed? [pnmed_longer]x
 - 2. Have you used prescription pain medications that were prescribed to someone else? [pnmed_othersrx]x
 - b. Compute the change at 6 months post-intervention (change of opioid misusep) of group-level data collected from groups of health

All endpoints are independent outcomes.

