Pharmacy, Health Benefits	Does your organization's pharmacy benefit set limits for coverage of prescription opioids (i.e. number of day's supply, maximum dose, type of opioids allowable)?	Y/N	CDC Guideline for Prescribing Opioids for Chronic Pain	28
	Does your organization's pharmacy benefit manager include an opioid prescription monitoring program?	Y/N	Structuring Health Benefits for Drug Misuse Issues	28
	Does your organization's pharmacy benefit cover medication for opioid addiction treatment (i.e. buprenorphine) as a long-term treatment?	Y/N	MAT for Opiate Dependence	28
EAP or MAP	Does your contracted or hired EAP/MAP participate in your organization's programs (i.e. deliver customized training, help with return to work management after treatment)?	Y/N	EASNA: EAP Purchaser Guide	32
Legal Concerns	Does your organization's return to work policy cover employees with substance use disorder?	Y/N	JAN-Drug Addiction	34

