Employees with opioid use disorder may have experienced a dependency to opioids for many years, so treatment and recovery may require receiving inpatient and/or outpatient treatments. In addition to detox and medication for addiction, employees should receive behavioral health counseling to learn how to manage their substance use within the context of their life [82]. This process will take time. Risk of relapse is lessened with ongoing treatments and support [57] and if the cost of treatment is covered by their health plan [83]. The employee would also benefit from having a flexible work schedule and if necessary, paid time off to allow them to attend outpatient treatment.

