 - 1. Serial prescriptions (most common scenario)
 - a. Start with all opioid first fills (including unlinked and linked with medical claims, using the process above)

- b. Arrange all fills by UID and fill date
 - c. Assign fills to claims that 1) occur after a claim with a linked opioid fill, and 2) opioid fill date is no more than 30 days after previous fill runout date (fill date + days supply)
2. Refills specified in the pharmacy data
 - a. Join opioid refills (from 1b above) with the first fills using prescription identifier ("RXNUM").
 - b. Assign claim information from first fills to linked refills

Variable definitions

- e. Opioid-related variables. These variables were generated using information from the medical claims and pharmacy fill data from the health fund and the CDC opioid file "CDC opioid NDC_oral MME conversion_update_2020.xlsx". The CDC file was merged with health fund pharmacy fill data on NDC
 - i. Medication assisted treatment (MAT): Drug name contained "methadone" or "buprenorphine" in either file or drug description was "ANTIDOTES AND SPECIFIC ANTAGONISTS" in the pharmacy fill file
 1. This strategy picks up buprenorphine, suboxone, zubsolv, naltrexone, methadone, narcan, and vivitrol
 - ii. Opioid: pharmacy class was "opioid" in the CDC file, and the drug was not already identified as MAT (see above)
 - iii. OUD: ever ICD-10 code "T40x" or "F11x" on a medical claim or identified as MAT (see above)
 - iv. Days supply > 7 days: based on "days supply" as provided in fill data
 - v. MME/day: Instructions for calculation are in CDC file. Formula is "strength per unit" * "average quantity per day" * "MME conversion factor"
 - vi. Overlapping Rx: Date opioid fill is within previous days supply (current fill date < previous fill date + days supply)
 1. When the previous prescription is a "short course" (the prescription window is encompassed by prescription before it), the prescription before the short course is used in evaluation
 - vii. Chronic use (>60 days supply in a 90 day window)
 1. For each worker time is divided into 90 day "cycles", starting with the date of the first opioid fill
 2. Days supply is totaled within the 90 day cycle
 3. If the individual had opioid fills later than 90 days after the first fill, a new cycle is started and the process starts over
 4. When workers have multiple opioids filled on the same day, use the longest days supply in calculations

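### The claims outcomes count every worker flagged in a period, so carried-over OUD and chronic-use cases dilute any fall in new cases, which is the guidelines' stated goal

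*Combined protocol and SAP*

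**What the plan says.** - **Goal.** Section 4.3 states that the "overall goal of the guidelines are to reduce the incidence of opioid misuse and opioid use disorder"; the same sentence adds fewer missed work days and more willingness to seek treatment. Section 2.2 also presents guidelines as a way to prevent new cases.
- **Endpoint.** The synopsis defines the claims endpoint as "the change in the proportion of workers with opioid misuse, opioid use disorder and opioid overdose: administrative data". Section 9.4.2 instructs: "Compute statistics for baseline period (06/01/2019-05/31/2022) and follow-up (06/01/2022-05/31-2023".
- **Case definitions.** Section 9.4.2 gives "Chronic opioid use- more than 60 days supply in a 90 day window". The data-management appendix in Section 10.2 defines OUD as ever having a T40 or F11 code "on a medical claim or identified as MAT (see above", where MAT is medication-assisted treatment.
- **What is absent.** The appendix excludes members only for missing eligibility or termination dates, or for cancer. Opioid naivety is derived per claim in the linkage step but enters no endpoint.
- **Intended reading.** Section 9.4.1 compares the two periods, adjusting for their length by an unstated method, "to show a reduction in impaired health or behaviors that may be due to implementation of the intervention".
- **Duration.** The guidelines say "Employees with opioid use disorder may have experienced a dependency to opioids for many years", and their needs assessment asks whether the pharmacy benefit will "cover medication for opioid addiction treatment (i.e. buprenorphine) as a long-term treatment". They also discuss members already receiving opioids for long-term pain.

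**The concern.** A preventive programme can lower the number of new cases. It cannot prevent a case that already exists. A member diagnosed in 2019 and still treated in 2023 is a case in both periods, so the follow-up proportion mixes new onset with carry-over, and the plan has no way to separate them.

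The OUD flag has a further difficulty. The guidelines ask funds to cover MAT and to screen for substance use, and an MAT fill is itself an OUD flag. A fund that follows this advice may bring existing, previously unseen cases into the count.

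Two things are at stake: whether a change in the claims proportions says anything about prevention, and whether the rates passed to the future trial (Sections 9.1 and 9.2) describe new onset or a mixture.

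**Working it through.** **Inputs.** The documents give the case definitions, the two periods (36 and 12 months) and the planned claims population. That population reproduces from Section 9.2: 3 funds × 10,200 = 30,600. (The synopsis gives 33300; the two should be reconciled, but nothing here depends on it.) The documents give no flag rates, carry-over share or effect size, so those below are assumptions. OUD is taken as ever flagged within the period.

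**1. Dilution on equal windows.** Let r be the relative cut in new cases and s the share of flagged members who would be carried over absent an effect. Carried-over cases do not change, so

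relative fall in flagged proportion = r × (1 − s).

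With r = 30%:

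| s | Calculation | Fall shown |
|---|---|---|
| 10% | 0.30 × 0.90 | 27% |
| 25% | 0.30 × 0.75 | 22.5% |
| 50% | 0.30 × 0.50 | 15% |
| 75% | 0.30 × 0.25 | 7.5% |
| 90% | 0.30 × 0.10 | 3% |

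If s is instead the share observed at follow-up, after the effect, the fall is r(1 − s)/(1 − rs): about 18%, 10% and 4% at s = 50%, 75% and 90%. The message is the same.

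**2. When an apparent rise can occur.** The formula in step 1 is never negative, so something else is needed. Let P be the share already flagged at the start of a period and I the yearly share newly flagged, both steady and with no exits.

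- *Dividing by period length.* Baseline per year is (P + 3I)/3; follow-up is P + 0.7I. Follow-up is higher when (2/3)P > 0.3I, that is, P > 0.45 × I. At assumed P = 1% and I = 0.5%, baseline is 2.5%/3 = 0.833% and follow-up is 1.35%, a ratio of 1.62 despite a true 30% cut. With no effect the ratio is 1.5%/0.833% = 1.80. Undivided proportions err the other way: 1.5%/2.5% = 0.60 with no effect.
- *More MAT or diagnosis flags.* At the same P and I with 30,600 members, the cut avoids 0.3 × 0.005 × 30,600 ≈ 46 new flags. Carried-over members number 0.01 × 30,600 = 306. Newly flagged existing cases equal in number to 15% of 306, about 46, would cancel the gain.

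**3. Consequence for planning.** At the same P and I on equal one-year windows, the flagged proportion moves from 1.5% to 1.35% (ratio 0.90), while new onset moves from 0.5% to 0.35% (ratio 0.70). With 30,600 per period and a two-sided 5% level, illustrative power is 0.35 against 0.81. This treats the periods as independent and ignores clustering by fund, so only the contrast is informative.

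**4. Does the fix fit the data?** Each one-year window needs 24 prior months. The comparison year June 2021–May 2022 with lookback June 2019–May 2021 uses exactly 36 baseline months. The follow-up year June 2022–May 2023 takes June 2020–May 2022 as its lookback.

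**The case against.** The strongest reply is that the proportion of workers is the trial's own endpoint, stated consistently in the synopsis and Sections 3 and 9.1. Incidence appears in the justification for the intervention, in a sentence that also covers missed work and help-seeking. The guidelines span prevention, treatment and recovery, so a measure that includes existing cases is legitimate. This stands: the period proportion is not a wrong endpoint. It simply does not measure incidence.

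A reader might infer that the plan would judge a fund a failure if its flagged proportion rose. The documents do not support that. Section 3 defines success as recruiting three funds and collecting the measures, and Section 9.1 rules out formal hypothesis testing. The wording in Section 9.4.1 is interpretive, not a success criterion.

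A reader might also infer that carry-over alone can reverse a preventive effect. It only dilutes; an apparent rise needs one of the two mechanisms in step 2 of the working.

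Nor does the evidence of long duration extend equally to claims-based misuse, which consists of overlapping fills or same-day fills from different providers, or to acute T40 events. The wording on OUD duration is itself conditional. At s = 10% or 25% the dilution is minor, and nothing in the documents favours a high s.

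**Conclusion.** The point holds for OUD and chronic use. The guidelines' goal is stated as incidence, no planned claims outcome estimates it, and carried-over cases dilute any fall in new cases by the factor 1 − s. A 30% cut would show as anything from 27% to 3% for s between 10% and 90%. The true s is unknown, so the actual loss may be small or large.

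This rests on carried-over cases being unaffected by the intervention and on equal windows. The unequal windows and the counting of MAT as OUD can push the result further, in directions set out above.

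The trial is descriptive and unpowered, so no formal conclusion is invalidated. The harm is to the interpretation offered in Section 9.4.1 and to the rates used to plan the future trial. The change is worth making because it is cheap.

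**What to change.** Keep the period proportions as the stated endpoint and add to Section 9.4.2, as descriptive outcomes:

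1. New-onset OUD and new-onset chronic use (misuse optional) in two one-year windows: June 2022–May 2023 with lookback June 2020–May 2022, and June 2021–May 2022 with lookback June 2019–May 2021. Include members eligible and free of the relevant flag throughout the lookback.
2. A 12-month lookback as a sensitivity analysis.
3. Previously flagged members reported separately, and F11/T40 diagnoses shown apart from MAT fills.
4. A sentence in Section 9.4.1 that any statement about prevention rests on the new-onset results, and that a rise in MAT-treated cases is not by itself read as worsening.

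**Cost.** SAP wording and one extra derivation from dated claims (Section 9.4.8) and census eligibility dates (appendix), which the plan already uses. Census dates must run through May 2023; the appendix's inclusion period stops at May 2022.

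**Downsides.** Eligibility is tied to hours worked and construction work is intermittent (Section 2.2), so a 24-month lookback shrinks the cohort and selects steadier workers, by an amount the documents do not let us estimate. First-flagged OUD may still include old cases newly detected. The follow-up year depends on 12-month claims, and Sections 4.1 and 7.1 make 12-month collection conditional on time.

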4.4 END-OF-STUDY DEFINITION

The end-of-study is defined as the collection of 6-months (or 12-months) of data has been collected from all enrolled union health funds OR the end of the funding period (including no-cost extension time). Since

this is a feasibility trial, it is not known if three organizations will be successfully recruited and if it will be feasible to collect all data for outcomes (including administrative claims and workers surveys) by the end of the funding period.

5 STUDY POPULATION

The study population are members of the participating union health funds from the construction trades. All of the member workers of the enrolled health funds will be considered eligible participants for the study. For administrative claims data, this will include all members who were benefits eligible from May 2019 through the end of the study period (May 2023). For worker surveys, all active members of the union will be eligible and invited to participate. There will be no exclusions from eligibility.

The members of the union health funds will be at least 18 years of age, with no maximum age limit. The study population characteristics will reflect the demographics of the workforce, with approximately 8% female and 10% non-Caucasian.

5.1 INCLUSION CRITERIA

All members of the participating union health funds will be eligible for inclusion in the study. For administrative data, this will include benefits-eligible members of the union health fund from May 2019-May 2023. For worker surveys, this will include members of the union from May 2022-May 2023. The members will be at least 18 years of age, as that is an age requirement of the union. There are no other demographic restrictions.

5.2 EXCLUSION CRITERIA

There is no exclusion criteria for participation among the members of the participating union health funds. Each participating health fund must sign a data transfer and use agreement to provide the research team access to the administrative claims data and share requests to the members to complete a worker survey. Participating health funds must also be willing to review the workplace opioid guidelines for trial and to have regular meetings with the research team to share their plans related to using the intervention (guidelines).

Union health funds that do not complete a data transfer and use agreement, and are unwilling to facilitate surveying their members and are unwilling to trial the intervention will be excluded from participation.

